Appendix 3. Algorithm for Calculating the CHAQ

The Childhood Health Assessment Questionnaire (HAQ) has been adapted from the Stanford Health Assessment Questionnaire. The Stanford HAQ assesses four outcome dimensions: disability, discomfort and pain, drug side effects, and dollar costs. Disability is measured in the categories of dressing, arising, eating, walking, hygiene, grip, and activities. Discomfort is determined by the presence of pain and its severity. The HAQ is either parent- or self-administered. Parents are reliable proxy-reporters for their child's functional status, describe below is the parent-administered format. Parents are given the questionnaire and asked to complete it without additional instructions.

Disability Index – Daily Function

General Description:

This section is designed to assess the patient's functional ability over the past week. It is composed of eight domains, each of which has at least two component questions. Parents are also asked to indicate the use of any aids or devices or if the child needs help from another person for any of these activities.

The eight domains are: dressing and grooming, arising, eating, walking, hygiene, reach, grip, and activities. For each of these domains, parents are asked to record the amount of difficulty their child may have. Parents are requested to note only those difficulties that are caused by arthritis.

The time frame is over the past week. By repeating the questionnaire at specific time periods we can look at the patterns of function.

Scoring and Coding:

Possible responses for the component questions are:

Without any difficulty = 0

With some difficulty = 1

With much difficulty = 2

Unable to do = 3.

The patient must have a score for at least 6 of the 8 domains. If there are less than six domains completed, a CHAQ cannot be computed. The highest score for any component question determines the score for that category. If a component question is left blank, then the score for that category is determined by the remaining completed question(s). If all component questions are blank, then the category is left blank.

If either devices and/or help from another person is checked for a category, the score = 2. This may determine the score unless the score on any other component question = 3. For example, the response to "Dress yourself..." is with Some difficulty (score = 1). The parent has checked the use of a device for dressing, thereby increasing the score to 2. The response to "Shampoo your

hair" is Unable to do (score = 3). Therefore, the score for the Dressing category is 3. The index is calculated by adding the scores for each of the domains and dividing by the number of domains answered. This gives a score in the 0 to 3.0 range.

Devices associated with each category:

CHAQ Category	Companion aids or devices item
Dressing and Grooming	Devices used for dressing (button hook, zipper pull, long handled shoe horn, etc.)
Arising	Built up or special chair
Eating	Built up or special utensils
Walking	Cane, walker, crutches, wheelchair
Hygiene	Raised toilet seat, bathtub seat, bathtub bar, long-handled appliances in bathroom
Reach	Long handled appliances for reach
Grip	Jar opener (for jars previously opened)

Devices written in the "Other" sections are considered only if they would be used for any of the stated domains.

Discomfort – Index or VAS

General Description:

This question is designed to obtain information about the presence or absence of arthritis-related pain and its severity. The time frame is in the past week. The Discomfort Index of the CHAQ includes (Ruperto et al. 2001):

- Parent's Global Assessment of Well-being
 - This is a component of the JIA ACR 30 core response set
 - The instrument uses a 0 to 100 mm VAS where 0 = "very well" and 100 = "very poor"
- Pain assessment due to illness
 - The question uses a 0 to 100 mm VAS where 0 = "no pain" and 100 = "very severe pain"

Appendix 4. Algorithm for Calculating Total and Tender Dactylitic Digit

Dactylitic digits are evaluated and recorded as either non-evaluable, or if evaluable, then if tenderness is present or absent. In total, 20 dactylitic joints are assessed.

The total and tender dactylitic digit scores will be calculated by summing all dactylitic joints, and those checked to have tenderness present, respectively. If at least half but not all the dactylitic joints are evaluable, then the observed prorated joint count will be calculated instead. The prorated scores for tenderness count will be adjusted based upon the number of evaluable dactylitic joints: the counted score will be multiplied by 20 then divided by the number of dactylitic joints evaluated (excluding non-evaluable dactylitic joints and any dactylitic joints with a missing response). For example: if only 15 of the 20 dactylitic joints are assessed to be evaluable at a visit, and 12 of those 15 are tender, the prorated joint count is $(12/15)*20=36.27$ (not 12). The prorated joint count will be rounded up to the next integer and be used in calculating the percent change from baseline in tenderness count. If less than half of the dactylitic joints are evaluable, the tender dactylitic joint count is missing.

The Total Dactylitic Digit score is the sum of dactylitic joints.

The Tender Dactylitic Digit score is the sum of tender dactylitic joints.

Change from baseline: observed total dactylitic digit at visit minus baseline Total Dactylitic Digit

Change from baseline: observed tender dactylitic digit at visit minus baseline Tender dactylitic digit

% Improvement in Total Dactylitic Digit score calculated as:

$$\% \text{ improvement from baseline} = 100 \times \frac{(\text{Baseline Total Dactylitic Digit score} - \text{Observed Total Dactylitic Digit score})}{\text{Baseline Total Dactylitic Digit score}}$$

% Improvement in Tender Dactylitic Digit score calculated as:

$$\% \text{ improvement from baseline} = 100 \times \frac{(\text{Baseline Tender Dactylitic Digit score} - \text{Observed Tender Dactylitic Digit score})}{\text{Baseline Tender Dactylitic Digit score}}$$

Appendix 5. Anti-infective Medications and Anatomical Therapeutic Chemical (ATC) Code List and Programming Guide

This appendix provides the code list of ATC of anti-infective medications and the programming guidance.

ATC Code	ATC Level	ATC Description (Based on ATC Dictionary 18JAN2016)
A01AB	4	ANTIINFECTIVES AND ANTISEPTICS FOR LOCAL ORAL TREA
A02BD	4	COMBINATIONS FOR ERADICATION OF HELICOBACTER PYLOR
A07A	3	INTESTINAL ANTIINFECTIVES
A07AA	4	ANTIBIOTICS
A07AB	4	SULFONAMIDES
A07AC	4	IMIDAZOLE DERIVATIVES
A07AX	4	OTHER INTESTINAL ANTIINFECTIVES
B05CA	4	ANTIINFECTIVES
C05AB	4	ANTIBIOTICS
D01	2	ANTIFUNGALS FOR DERMATOLOGICAL USE
D01A	3	ANTIFUNGALS FOR TOPICAL USE
D01AA	4	ANTIBIOTICS
D01AC	4	IMIDAZOLE AND TRIAZOLE DERIVATIVES
D01AE	4	OTHER ANTIFUNGALS FOR TOPICAL USE
D01B	3	ANTIFUNGALS FOR SYSTEMIC USE
D01BA	4	ANTIFUNGALS FOR SYSTEMIC USE
D06	2	ANTIBIOTICS AND CHEMOTHERAPEUTICS FOR DERMATOLOGIC
D06A	3	ANTIBIOTICS FOR TOPICAL USE
D06AA	4	TETRACYCLINE AND DERIVATIVES
D06AX	4	OTHER ANTIBIOTICS FOR TOPICAL USE
D06B	3	CHEMOTHERAPEUTICS FOR TOPICAL USE
D06BA	4	SULFONAMIDES
D06BB	4	ANTIVIRALS
D06BX	4	OTHER CHEMOTHERAPEUTICS
D06C	3	ANTIBIOTICS AND CHEMOTHERAPEUTICS, COMBINATIONS
D07C	3	CORTICOSTEROIDS, COMBINATIONS WITH ANTIBIOTICS
D07CA	4	CORTICOSTEROIDS, WEAK, COMBINATIONS WITH ANTIBIOTICS
D07CB	4	CORTICOSTEROIDS, MODERATELY POTENT, COMBINATIONS WITH ANTIBIOTICS
D07CC	4	CORTICOSTEROIDS, POTENT, COMBINATIONS WITH ANTIBIOTICS
D07CD	4	CORTICOSTEROIDS, VERY POTENT, COMBINATIONS WITH ANTIBIOTICS
D09AA	4	MEDICATED DRESSINGS WITH ANTIINFECTIVES
D10AF	4	ANTIINFECTIVES FOR TREATMENT OF ACNE
G01AA	4	ANTIBIOTICS
G01AC	4	QUINOLINE DERIVATIVES
G01AE	4	SULFONAMIDES

ATC Code	ATC Level	ATC Description (Based on ATC Dictionary 18JAN2016)
G01AF	4	IMIDAZOLE DERIVATIVES
G01AG	4	TRIAZOLE DERIVATIVES
G01AX	4	OTHER ANTIINFECTIVES AND ANTISEPTICS
G01BA	4	ANTIBIOTICS AND CORTICOSTEROIDS
G01BC	4	QUINOLINE DERIVATIVES AND CORTICOSTEROIDS
G01BE	4	SULFONAMIDES AND CORTICOSTEROIDS
G01BF	4	IMIDAZOLE DERIVATIVES AND CORTICOSTEROIDS
G04AB	4	QUINOLONE DERIVATIVES (EXCL. J01M)
G04AC	4	NITROFURAN DERIVATIVES
G04AG	4	OTHER URINARY ANTISEPTICS AND ANTIINFECT
G04AH	4	SULFONAMIDES IN COMBINATION WITH OTHER DRUGS
G04AK	4	URINARY ANTISEPT&ANTIINF, COMB EXCL SULFONAMIDES
J01	2	ANTIBACTERIALS FOR SYSTEMIC USE
J01A	3	TETRACYCLINES
J01AA	4	TETRACYCLINES
J01B	3	AMPHENICOLS
J01BA	4	AMPHENICOLS
J01C	3	BETA-LACTAM ANTIBACTERIALS, PENICILLINS
J01CA	4	PENICILLINS WITH EXTENDED SPECTRUM
J01CE	4	BETA-LACTAMASE SENSITIVE PENICILLINS
J01CF	4	BETA-LACTAMASE RESISTANT PENICILLINS
J01CG	4	BETA-LACTAMASE INHIBITORS
J01CR	4	COMBINATIONS OF PENICILLINS, INCL. BETA-LACTAMASE
J01D	3	OTHER BETA-LACTAM ANTIBACTERIALS
J01DA	4	CEPHALOSPORINS AND RELATED SUBSTANCES
J01DB	4	FIRST-GENERATION CEPHALOSPORINS
J01DC	4	SECOND-GENERATION CEPHALOSPORINS
J01DD	4	THIRD-GENERATION CEPHALOSPORINS
J01DE	4	FOURTH-GENERATION CEPHALOSPORINS
J01DF	4	MONOBACTAMS
J01DH	4	CARBAPENEMS
J01DI	4	OTHER CEPHALOSPORINS
J01E	3	SULFONAMIDES AND TRIMETHOPRIM
J01EA	4	TRIMETHOPRIM AND DERIVATIVES
J01EB	4	SHORT-ACTING SULFONAMIDES
J01EC	4	INTERMEDIATE-ACTING SULFONAMIDES
J01ED	4	LONG-ACTING SULFONAMIDES
J01EE	4	COMBINATIONS OF SULFONAMIDES AND TRIMETHOPRIM, INC
J01F	3	MACROLIDES, LINCOSAMIDES AND STREPTOGRAMINS
J01FA	4	MACROLIDES
J01FF	4	LINCOSAMIDES
J01FG	4	STREPTOGRAMINS
J01G	3	AMINOGLYCOSIDE ANTIBACTERIALS
J01GA	4	STREPTOMYCINS
J01GB	4	OTHER AMINOGLYCOSIDES
J01M	3	QUINOLONE ANTIBACTERIALS

ATC Code	ATC Level	ATC Description (Based on ATC Dictionary 18JAN2016)
J01MA	4	FLUOROQUINOLONES
J01MB	4	OTHER QUINOLONES
J01R	3	COMBINATIONS OF ANTIBACTERIALS
J01RA	4	COMBINATIONS OF ANTIBACTERIALS
J01WA	4	HERBAL ANTIBACTERIALS FOR SYSTEMIC USE
J01WB	4	HERBAL URINARY ANTISEPTICS AND ANTIINFECTIVES
J01X	3	OTHER ANTIBACTERIALS
J01XA	4	GLYCOPEPTIDE ANTIBACTERIALS
J01XB	4	POLYMYXINS
J01XC	4	STEROID ANTIBACTERIALS
J01XD	4	IMIDAZOLE DERIVATIVES
J01XE	4	NITROFURAN DERIVATIVES
J01XX	4	OTHER ANTIBACTERIALS
J02	2	ANTIMYCOTICS FOR SYSTEMIC USE
J02A	3	ANTIMYCOTICS FOR SYSTEMIC USE
J02AA	4	ANTIBIOTICS
J02AB	4	IMIDAZOLE DERIVATIVES
J02AC	4	TRIAZOLE DERIVATIVES
J02AX	4	OTHER ANTIMYCOTICS FOR SYSTEMIC USE
J04AA	4	AMINOSALICYLIC ACID AND DERIVATIVES
J04AB	4	ANTIBIOTICS
J04AC	4	HYDRAZIDES
J04AK	4	OTHER DRUGS FOR TREATMENT OF TUBERCULOSIS
J04AM	4	COMBINATIONS OF DRUGS FOR TREATMENT OF TUBERCULOSIS
J04B	3	DRUGS FOR TREATMENT OF LEPRA
J04BA	4	DRUGS FOR TREATMENT OF LEPRA
J05	2	ANTIVIRALS FOR SYSTEMIC USE
J05A	3	DIRECT ACTING ANTIVIRALS
J05AA	4	THIOSEMICARBAZONES
J05AB	4	NUCLEOSIDES AND NUCLEOTIDES EXCL. REVERSE TRANSCRI
J05AC	4	CYCLIC AMINES
J05AD	4	PHOSPHONIC ACID DERIVATIVES
J05AE	4	PROTEASE INHIBITORS
J05AF	4	NUCLEOSIDE AND NUCLEOTIDE REVERSE TRANSCRIPTASE IN
J05AG	4	NON-NUCLEOSIDE REVERSE TRANSCRIPTASE INHIBITORS
J05AH	4	NEURAMINIDASE INHIBITORS
J05AR	4	ANTIVIRALS FOR TREATMENT OF HIV INFECTIONS, COMBIN
J05AX	4	OTHER ANTIVIRALS
P01A	3	AGENTS AGAINST AMOEBIASIS AND OTHER PROTOZOAL DISE
P01AA	4	HYDROXYQUINOLINE DERIVATIVES
P01AB	4	NITROIMIDAZOLE DERIVATIVES
P01AC	4	DICHLOROACETAMIDE DERIVATIVES
P01AR	4	ARSENIC COMPOUNDS
P01AX	4	OTHER AGENTS AGAINST AMOEBIASIS AND OTHER PROTOZOA
P01BA	4	AMINOQUINOLINES
P01BC	4	METHANOLQUINOLINES

ATC Code	ATC Level	ATC Description (Based on ATC Dictionary 18JAN2016)
P01BD	4	DIAMINOPYRIMIDINES
P01BE	4	ARTEMISININ AND DERIVATIVES, PLAIN
P01BF	4	ARTEMISININ AND DERIVATIVES, COMBINATIONS
P01BX	4	OTHER ANTIMALARIALS
P01C	3	AGENTS AGAINST LEISHMANIASIS AND TRYPANOSOMIASIS
P01CA	4	NITROIMIDAZOLE DERIVATIVES
P01CB	4	ANTIMONY COMPOUNDS
P01CC	4	NITROFURAN DERIVATIVES
P01CD	4	ARSENIC COMPOUNDS
P01CX	4	OTHER AGENTS AGAINST LEISHMANIASIS AND TRYPANOSOMI
P02	2	ANTHELMINTICS
P02B	3	ANTITREMATODALS
P02BA	4	QUINOLINE DERIVATIVES AND RELATED SUBSTANCES
P02BB	4	ORGANOPHOSPHOROUS COMPOUNDS
P02BX	4	OTHER ANTITREMATODAL AGENTS
P02C	3	ANTINEMATODAL AGENTS
P02CA	4	BENZIMIDAZOLE DERIVATIVES
P02CB	4	PIPERAZINE AND DERIVATIVES
P02CC	4	TETRAHYDROPYRIMIDINE DERIVATIVES
P02CE	4	IMIDAZOTHIAZOLE DERIVATIVES
P02CF	4	AVERMECTINES
P02CX	4	OTHER ANTINEMATODALS
P02D	3	ANTICESTODALS
P02DA	4	SALICYLIC ACID DERIVATIVES
P02DW	4	HERBAL ANTICESTODALS
P02DX	4	OTHER ANTICESTODALS
P02WA	4	HERBAL ANTHELMINTICS
P03A	3	ECTOPARASITICIDES, INCL. SCABICIDES
P03AA	4	SULFUR CONTAINING PRODUCTS
P03AB	4	CHLORINE CONTAINING PRODUCTS
P03AC	4	PYRETHRINES, INCL. SYNTHETIC COMPOUNDS
P03AX	4	OTHER ECTOPARASITICIDES, INCL. SCABICIDES
P03BA	4	PYRETHRINES
R02AB	4	ANTIBIOTICS
S01A	3	ANTIINFECTIVES
S01AA	4	ANTIBIOTICS
S01AB	4	SULFONAMIDES
S01AD	4	ANTIVIRALS
S01AE	4	FLUOROQUINOLONES
S01AX	4	OTHER ANTIINFECTIVES
S01C	3	ANTIINFLAMMATORY AGENTS AND ANTIINFECTIVES IN COMB
S01CA	4	CORTICOSTEROIDS AND ANTIINFECTIVES IN COMBINATION
S01CB	4	CORTICOSTEROIDS/ANTIINFECTIVES/MYDRIATICS IN COMBI
S01CC	4	ANTIINFLAMMATORY AGENTS, NON-STEROIDS AND ANTIINFECTIVES
S02A	3	ANTIINFECTIVES
S02AA	4	ANTIINFECTIVES

ATC Code	ATC Level	ATC Description (Based on ATC Dictionary 18JAN2016)
S02C	3	CORTICOSTEROIDS AND ANTIINFECTIVES IN COMBINATION
S02CA	4	CORTICOSTEROIDS AND ANTIINFECTIVES IN COMBINATION
S03A	3	ANTIINFECTIVES
S03AA	4	ANTIINFECTIVES
S03C	3	CORTICOSTEROIDS AND ANTIINFECTIVES IN COMBINATION
S03CA	4	CORTICOSTEROIDS AND ANTIINFECTIVES IN COMBINATION

Abbreviation: ATC = World Health Organization Collaborating Centre for Drug Statistics Methodology (WHOCC)
Anatomical Therapeutic Chemical (ATC) classification system.

For the above list, the higher level of ATC includes all the lower levels under that level; for example, level 2 term includes all the level 3 terms under it, level 3 term includes all the level 4 terms under it. Therefore, for programming simplicity, the table below provides all the required ATC codes by highest level.

ATC Level 2	ATC Level 3	ATC Level 4
		A01AB
		A02BD
	A07A	
		B05CA
		C05AB
D01		
D06		
	D07C	
		D09AA
		D10AF
		G01AA
		G01AC
		G01AE
		G01AF
		G01AG
		G01AX
		G01BA
		G01BC
		G01BE
		G01BF
		G04AB
		G04AC
		G04AG
		G04AH
		G04AK
J01		
J02		
		J04AA
		J04AB
		J04AC
		J04AK

ATC Level 2	ATC Level 3	ATC Level 4
		J04AM
	J04B	
J05		
	P01A	
		P01BA
		P01BC
		P01BD
		P01BE
		P01BF
		P01BX
	P01C	
P02		
	P03A	
		P03BA
		R02AB
	S01A	
	S01C	
	S02A	
	S02C	
	S03A	
	S03C	

Abbreviation: ATC = World Health Organization Collaborating Centre for Drug Statistics Methodology (WHOCC)
Anatomical Therapeutic Chemical (ATC) classification system.

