9.1.4. Exploratory Efficacy Assessments

9.1.4.1. Total and Tender Dactylitic Digit Count

Dactylitis is defined as swelling of a digit that extends beyond the joint margin (Petty et al. 2004). The assessor will first assess the participant for the presence of dactylitis and will record the total number of dactylitic digits in the participant's hands and feet (dactylitic digit count range 0 to 20). Tenderness will be assessed, and the number of tender dactylitic digits will be recorded (tender dactylitic digit count range 0 to 20) (Helliwell et al. 2005).

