Leeds Enthesitis Index (LEI) for patients with baseline enthesitis (LEI >0)	Yes		
Total Dactylitic Digit Count for patients with ≥1 Dactylitic Digit	Yes		

Variable	Continuous Measure Summary	Categorical / Interval Summary	Subgroup Analysis
Tender Dactylitic Digit Count for patients with ≥ 1 Tender Dactylitic Digit	Yes		
PASI total score ^f for patients who have baseline psoriatic lesion(s) involving Body Surface Area (BSA) $\geq 3\%$	Yes		
Percentage of BSA for patients who have baseline plaque psoriasis	Yes		
Percentage of BSA category for patients who have baseline plaque psoriasis	No	$<3\%, \geq 3\%$	
Methotrexate (MTX) use at baseline	No	Yes or no	Yes
MTX dose among patients who take MTX concomitantly	Yes		
Sulfasalazine use at baseline	No	Yes or no	Yes
Sulfasalazine dose among patients who take Sulfasalazine concomitantly	Yes		
Previous biologic disease-modifying antirheumatic drugs (bDMARDs)	No	Never used or Ever used	
Previous conventional disease-modifying antirheumatic drugs (csDMARDs ^g)	No	Never used, used 1 therapy, 2 therapies, ≥ 3 therapies	
Concomitant csDMARDs ^h	No	Yes or no	
Concomitant NSAIDs ^d	No	Yes or no	
Concomitant oral corticosteroids	No	Yes or no	
Children's Depression Inventory 2 SR(S) (CDI-2)	Yes		
Children's Depression Inventory 2 SR(S) (CDI-2)	No	$<6, \geq 6$	
Columbia Suicide Severity Rating Scale (C-SSRS) since last assessed	No	Suicidal ideation, Suicidal behavior, Suicidal ideation or behavior	
Tanner Stage Scale	No	Female (Breasts): B1, B2, B3, B4, B5 Male (Genitals): G1, G2, G3, G4, G5 Both (Pubic Hair)	

Variable	Continuous Measure Summary	Categorical / Interval Summary	Subgroup Analysis
		PH1, PH2, PH3, PH4, PH5	
Time since JIA symptom onset ^h (years)	Yes		
Time since JIA diagnosis ⁱ (years)	Yes		
Duration of JIA diagnosis (years) ^e categories	No	0 to <2 years, 2 to <5 years, 5 to <10 years, \geq 10 years	

Abbreviations: BMI = body mass index; CHAQ = Childhood Health Assessment Questionnaire; hsCRP = high-sensitivity C-Reactive Protein; ERA = enthesitis-related arthritis; ESR = erythrocyte sedimentation rate; HLA-B27 = human leukocyte antigen B27; JIA = juvenile idiopathic arthritis; JPsA = Juvenile Psoriatic Arthritis; NRS = Numeric Rating Scale; NSAID = nonsteroidal anti-inflammatory drug; PASI = Psoriasis Area and Severity Index; UK = United Kingdom; VAS = Visual Analogue Score.

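### SAP Appendix 4 rounds every prorated tender dactylitic count up to the next integer, which inflates low counts and can materially distort percent change from baseline

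*SAP*

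**What the plan says.** Protocol Section 9.1.4.1 places total and tender dactylitic digit counts among the exploratory efficacy assessments, each on a 0 to 20 scale. SAP Appendix 4 gives the derivation:

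- Number assessed: "In total, 20 dactylitic joints are assessed".
- When proration applies: "If at least half but not all the dactylitic joints are evaluable, then the observed prorated joint count will be calculated instead". With 20 digits that means 10 to 19 evaluable. Below 10 the tender count is missing.
- Scaling of the tender count: "the counted score will be multiplied by 20 then divided by the number of dactylitic joints evaluated".
- Rounding: "The prorated joint count will be rounded up to the next integer and be used in calculating the percent change from baseline". The sentence concerns the tender count and names only percent change. Appendix 4 does not say whether the reported count or the absolute change also uses the rounded value.
- Percent improvement is 100 times (baseline minus observed) divided by baseline.

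There is no nearest-integer alternative, no exception for a small fraction and no reason given for rounding upward. The baseline table in SAP Section 6.6.1 lists "Tender Dactylitic Digit Count for patients with ≥ 1 Tender Dactylitic Digit", so children who start with a single tender digit are included there.

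**The concern.** Proration on its own assumes that the digits that could not be evaluated are tender as often as those that could. Under that assumption it neither raises nor lowers the count on average. Rounding up adds a second step that works in one direction only. At low counts the correction is a small fraction of a digit, yet the rule turns it into a whole digit.

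The rounded count can enter percent change as either numerator or denominator, so the effect depends on which visit had the non-evaluable digit. At follow-up it exaggerates worsening or hides improvement. At baseline it exaggerates improvement. With the same number non-evaluable at both visits it can shrink a partial improvement. Because SAP Section 6.3.3 carries the last non-missing observation forward for continuous exploratory variables, an inflated value may also persist to later time points.

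**Working it through.** **Inputs.** From SAP Appendix 4: 20 digits; proration for m = 10 to 19 evaluable; prorated count 20k/m for k tender digits; rounding up to the next integer; percent improvement = 100 × (baseline − observed) / baseline, so that a positive value is improvement. From SAP Section 6.6.1: the smallest baseline count among children summarised for tender digits is 1.

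**The plan's own example.** Appendix 4 takes this case: "if only 15 of the 20 dactylitic joints are assessed to be evaluable at a visit, and 12 of those 15 are tender". Then (12/15) × 20 = 16. The SAP prints 36.27, which is above the scale maximum of 20 and is not reproduced. This is a separate slip. Because 16 is already an integer, the example does not show what the rounding does.

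**One non-evaluable digit (m = 19).** 20k/19 = k + k/19. For k = 1 to 18 the fraction lies strictly between 0 and 1, so rounding up gives k + 1. At k = 19 the prorated count is exactly 20, and at k = 0 it is 0; rounding changes neither. The part of the added digit due to rounding is 1 − k/19, which is 0.947 at k = 1 and falls as k rises.

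| Baseline (tender/evaluable) | Visit | Counts after rounding up | Improvement, rounded up | Improvement, unrounded |
|---|---|---|---|---|
| 1/20 | 1/19 | 1, 2 | 100 × (1−2)/1 = −100% | 100 × (1−1.053)/1 = −5.3% |
| 2/20 | 1/19 | 2, 2 | 100 × (2−2)/2 = 0% | 100 × (2−1.053)/2 = 47.4% |
| 1/19 | 1/20 | 2, 1 | 100 × (2−1)/2 = +50% | 100 × (1.053−1)/1.053 = +5.0% |
| 2/19 | 1/19 | 3, 2 | 100 × (3−2)/3 = 33.3% | 100 × (2.105−1.053)/2.105 = 50% |

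The distortion fades at higher counts. With an unchanged k, 20 evaluable digits at baseline and 19 at the visit, the rounded result is −50% at k = 2, −33.3% at k = 3, −20% at k = 5 and −10% at k = 10. It is −5.3% unrounded in every case.

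**More non-evaluable digits.** With k = 1 and any m from 11 to 19, 20/m lies between 1 and 2 and rounds to 2. A baseline of 1/20 therefore always scores −100%, where the unrounded value runs from −81.8% (m = 11) to −5.3% (m = 19). At m = 10 the prorated count is 2k, always an integer, so rounding has no effect. The affected range is therefore 1 to 9 non-evaluable digits.

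**Whole grid.** There are 145 combinations of m = 10 to 19 and k ≥ 1. In 31 the prorated count is an exact integer. In the other 145 − 31 = 114, rounding up inflates it. The mean excess over all 145 is 0.39 digit, and in 55 the result differs from nearest-integer rounding. These figures weight each combination equally and are not estimates for the trial population.

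**Effect on a group mean.** The documents do not give the number of children with tender dactylitis. Assume 5, 10 or 20 in a summary. One child scored −100% instead of −5.3% moves the mean by 94.7/5 = 18.9, 94.7/10 = 9.5 or 94.7/20 = 4.7 percentage points.

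**The case against.** Four points can be made for the other side.

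First, a reader might infer that the direction of change cannot be trusted for any affected child. That goes too far. Rounding up preserves order: if one prorated count is larger than another, its rounded value is never smaller. It can stretch a difference or flatten it to a tie, but it cannot turn improvement into worsening. Full resolution still scores 100%, and the same count with the same number of non-evaluable digits at both visits scores 0%.

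Second, a reader might blame rounding for all of the apparent change in a child whose observed count is constant. Part of it comes from proration and would remain after the fix: −5.3% for 1/20 to 1/19, and +5.0% for the reverse. Nor is the added digit necessarily false, since the state of a non-evaluable digit is unknown; if it is tender, 1 of 19 really is 2. That does not make rounding up a sound worst-case rule. It leaves 0 of 19 at 0 and gives 2 for 1 of 18, where the worst cases are 1 and 3. Applied at baseline, it favours treatment.

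Third, an explicit rounding convention contradicts nothing else in the documents, and nearest-integer rounding would be another option. This stands as a matter of form: the text is internally consistent. But no stated purpose needs an integer, and the unrounded value discards nothing and stays within 0 to 20 because k cannot exceed m.

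Fourth, the reach is limited. The count is exploratory and outside the JIA ACR core set, summaries beyond the primary Bayesian analysis are descriptive, and the exploratory tables in SAP Section 6.9.4 are redacted, so how prominently percent change is used cannot be seen. Protocol Section 9 also asks for the same assessor across visits where possible. All of this stands and keeps the point minor.

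**Conclusion.** The rule as written gives a one-directional upward error in the tender count whenever 1 to 9 digits are non-evaluable, at least one digit is tender and 20k/m is not an integer. At low counts the error in percent change is material: up to about 95 percentage points for one child with a baseline of 1 and a single non-evaluable digit at the visit.

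The arithmetic is exact and rests only on reading the rounding instruction literally. What it means for the results is unknown, because the documents give neither the frequency of non-evaluable digits nor the distribution of tender counts. The primary analysis is untouched. This is a minor point, worth correcting because the more accurate calculation is also the simpler one.

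**What to change.** In SAP Appendix 4, delete the instruction to round up and use the unrounded prorated count 20k/m in the percent change calculation. State that the same unrounded value is used for the reported tender count and for absolute change, which the appendix leaves open. The printed result of the worked example can be corrected to 16 in the same edit.

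The cost is one or two sentences in the SAP and one line of derivation code. The only drawback is an occasional non-integer count. The SAP already handles non-integer scores: PASI is analysed in steps of 0.1.
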